## **2.3 Potential Risks and Benefits**

### **2.3.1 Potential Risks**

This study is the first time that oxfendazole will be evaluated in humans. However, there are approved antiparasitic agents that have chemical similarities to oxfendazole. A single dose of the approved antiparasitic agent albendazole in humans is largely without side effects. More prolonged courses have been associated with liver abnormalities and bone marrow suppression. It has been associated with headache, gastrointestinal side effects (abdominal pain and nausea) in less than 10 % of subjects as well as rare allergic reactions (rash, urticaria, Stevens-Johnson syndrome) in less than 1 %. We expect that oxfendazole may have similar gastrointestinal events and rare allergic reactions, though this will be the first study in humans.

In animal studies, lower OXF doses and shorter periods of administration similarly result in no observable toxicity. At higher doses, the principal target organs are bone marrow and liver, WBC count rapidly recovers when OXF administration is discontinued. In the present study, only a single dose of oxfendazole will be administered to each subject.

In animal studies, fetotoxicity was reported and changes in the testes were seen.

Subjects will be closely monitored by history, physical examination and laboratory tests to assess safety and tolerability. Subjects will be carefully monitored for AEs and blood studies will be monitored to assess for any changes in the complete blood counts, liver and renal function and coagulation factors. As for any experimental drug, there may be side effects of oxfendazole that are not presently known. EKG studies will be performed to assess for cardiac effects.

This study will not recruit women of child bearing potential. Men will be counseled to use condoms and avoid pregnancy attempts for 4 months following drug administration.

There are no significant side effects from electrocardiogram (EKG) other than cosmetic annoyance from the glue employed to hold the leads. Venipuncture can result in pain or discomfort, and less likely, the possibility of bruising, or infection at the site, or fainting. Loss of confidential health information could occur.

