## 6.7 Handling of Abnormal Liver Function or Hematological Tests

Preclinical tests demonstrated changes in liver function and hematological tests. Subjects demonstrating a grade 3 or higher change in hematological parameters of absolute neutrophil count, hemoglobin, or platelet count or ALT or AST greater than 3 times the upper limit of normal or total bilirubin greater than 2 x the upper limit of normal will be asked to return for repeat testing within 72 hours of detection of the abnormal laboratory test. Repeat testing of any change in the complete blood count or absolute neutrophil count will require a repeat CBC with differential. Any change in the mentioned liver function tests (ALT, AST, or total bilirubin) will require repeat evaluation of all 4 liver tests. Testing should be repeated 2-3x per week until the laboratory value stabilizes or has returned to normal. All of the evaluations listed under “unscheduled visits” will apply for these return visits that require additional laboratory testing.

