## **8.5 Halting Rules**

Two sentinel subjects (1 study drug and 1 placebo) will be dosed and monitored 48 hours for adverse events prior to enrolling the remaining subjects in each cohort. If no drug-related SAE or grade 3 study drug related laboratory AE occurs in the sentinel subjects after 48 hours of observation, the remainder of the cohort may proceed with dosing.

An SRC composed of the Protocol Principal Investigator and Independent Safety Monitor will review blinded safety data for each completed cohort. Each new cohort will be dosed only after the 2-week safety data for the preceding group have been reviewed for the following events:

- The SRC will evaluate the safety data from each dose group and will allow continuation if there are no product related grade 3 AEs or if there are fewer than two product related grade 2 AEs identified.

Enrollment, dosing and study procedures will be halted for SMC review/recommendation if any of the following are reported:

- Any death occurring after administration of study drug through the subject's last study visit that was not the result of trauma or accident, regardless of relatedness to study product.
- Any subject experiences laryngospasm, bronchospasm, or anaphylaxis within 24 hours after administration of study product.
- Any subject experiences a study drug-related Stevens Johnson Syndrome.
- Two or more subjects experience generalized urticaria within 72 hours after administration of study product.
- Any subject experiences a study drug-related SAE from the time of receipt of study drug through the subject's last study visit.
- Any subject develops new EKG changes that are deemed significant by a reviewing cardiologist.
- Any subject develops grade 3 laboratory abnormalities deemed related to the study drug.
- The SRC members are not unanimous in their agreement to proceed to the next dosing group or cannot assess or do not unanimously agree on the relatedness of the adverse event to the study product.

If any of the halting rules are met following any subject receipt of study drug, the study will not continue with the remaining enrollments without a review by and recommendation from the SMC to proceed.

DMID retains the authority to suspend additional enrollment and study interventions/administration of study product during the entire study, as applicable.

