### **8.6.3 Safety Monitoring Committee (SMC)**

The SMC is an independent group of experts that advises DMID and the study investigators for many Phase 1 and smaller Phase 2 trials. The primary responsibility of the SMC is to monitor subject safety. The SMC is external to DMID, composed of at least three voting members. The SMC will consist of members with appropriate expertise to contribute to the interpretation of the data from this trial. Its activities will be delineated in an SMC charter that will delineate membership, responsibilities, and the scope and frequency of data reviews.

The SMC will review the safety data at the request of the SRC and if any of the halting rules are met.

The SMC will operate on a conflict-free basis independently of the study team. DMID and the SMC may convene ad hoc meetings of the SMC according to protocol criteria or if there are concerns that arise during the study. The ISM or principal investigator may request DMID to convene an ad hoc SMC meeting if a safety concern is identified. The SMC will have access to unblinded data during its closed session, if applicable.

A computerized system will be used to acquire any data regarding halting criteria throughout the study. If any of the halting rules are met, the study will not proceed with the remaining enrollments without a review by the SMC. After its assessment, the SMC will recommend continuation, modification, or termination of the clinical trial.

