## **SUPPLEMENTS/APPENDICES**

**APPENDIX A: SCHEDULE OF EVENTS**

Study Visit Number	1	2	3	4	5	6	7	8
Study Day (post administration)	D-28 to -1	D1	D2	D3	D4	D6	D8	D15
Visit/Contact Window (Days)	NA	NA	NA	NA	NA	+/- 1	+/- 1	+/- 2
Informed Consent	x							
Inclusion/Exclusion	x	x						
Medical History	x							
Interim Medical History		x						
Concomitant Medications	x	x	x	x	x	x	x	x
Vital signs 	x	x	x	x	x	x	x	x
Physical Examination	x	x						
HIV, HBC, HCV Testing	x							
Administration of oxfendazole/placebo 		x						
Counseling on avoidance of medications, recreational drugs and alcohol intake	x	x	x	x	x	x	x	

Study Visit Number	1	2	3	4	5	6	7	8
Study Day (post administration)	D-28 to -1	D1	D2	D3	D4	D6	D8	D15
Visit/Contact Window (Days)	NA	NA	NA	NA	NA	+/- 1	+/- 1	+/- 2
Targeted physical exam			x	x	x	x	x	x
Screening and Safety Labs (CBC, Blood Chemistry, Urinalysis) 	x 	x 		X 	x 		x 	x 
EKG	x				x		x	x
Blood draw for oxfendazole and metabolites 		x	x	x	x	x	x	x
Urine collection for oxfendazole, metabolites and creatinine 		x	x	x				
Assess/review for AEs and SAEs		x	x	x	x	x	x	x
Blood Volume for Day (Total Blood Volume for Study)	15 mL (15mL)	105 mL (120mL)	10 mL (130 mL)	10 mL (140 mL)	25 mL (165 mL)	10 mL (175 mL)	25 mL (200 mL)	25 mL (225 mL)

 Vital signs and laboratory values will be evaluated using the FDA Guidance for Industry "Toxicity Grading Scale for Healthy Adult and Adolescent Volunteers Enrolled in Preventive Vaccine Clinical Trials," September 2007.

 Volunteers will remain fasting for 2 hours after administration of drug/placebo.

 Any abnormal laboratory result arising after administration of oxfendazole, and of moderate or greater severity, will be followed until results return to baseline value or for the duration of safety follow-up.

 Safety laboratories include: WBC, absolute neutrophil count, eosinophil count, total platelet count, hemoglobin, sodium, potassium, chloride, bicarbonate, urea nitrogen, creatinine, prothrombin time, partial thromboplastin time, ALT, AST, total bilirubin, urine dipstick for protein and glucose

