Vomiting	No interference with activity or 1 - 2 episodes/24 hours	Some interference with activity or > 2 episodes/24 hours	Prevents daily activity or requires IV hydration
Diarrhea	2 - 3 loose or watery stools	4 - 5 loose or watery stools	6 or more loose or watery stools or requires IV hydration
Reactogenicity			
SYSTEMIC	Grade 1	Grade 2	Grade 3
Allergic Reaction	Pruritus without rash	Localized urticaria	Generalized urticaria; angioedema or anaphylaxis

Headache	No interference with activity	Repeated use of non-narcotic pain reliever > 24 hours or some interference with activity	Significant; any use of narcotic pain reliever or prevents daily activity
Fatigue	No interference with activity	Some interference with activity	Significant; prevents daily activity
Myalgia	No interference with activity	Some interference with activity	Significant; prevents daily activity
All Other Conditions	Grade 1	Grade 2	Grade 3
Illness or clinical adverse event (as defined according to applicable regulations)	No interference with activity	Some interference with activity not requiring medical intervention	Prevents daily activity and requires medical intervention

Laboratory Adverse Events			
Blood, Serum, or Plasma *	Grade 1	Grade 2	Grade 3
Sodium – Hyponatremia mEq/L	132 – <LLN	130 – 131	<130
Sodium – Hypernatremia mEq/L	>ULN – 148	149 – 150	>150
Potassium – Hyperkalemia mEq/L	>ULN – 5.2	5.3 – 5.4	>5.4
Potassium – Hypokalemia mEq/L	<LLN-3.1	<3.1 – 3.0	<3.0
CO 2	1-2 mEq/L above or below normal	3-4 mEq/L above or below normal	5 or more mEq/L above or below normal
Chloride	1-3 mEq/L above or below normal	4-5 mEq/L above or below normal	6 or greater above or below normal
Glucose – Hypoglycemia mg/dL	65 – 67	55 – 64	<55
Glucose – Hyperglycemia Fasting – mg/dL	>ULN - 120	121 – 130	>130
Glucose – Hyperglycemia Random – mg/dL	140 – 159	160 – 200	>200
Blood Urea Nitrogen mg/dL	23-26	27 – 31	> 31
Creatinine – mg/dL	>ULN – 1.7	1.8 – 2.0	>2.0
Calcium – hypocalcemia mg/dL	8.0 – <LLN	7.5 – 7.9	<7.5
Calcium – hypercalcemia mg/dL	>ULN – 11.0	11.1 – 11.5	>11.5
Magnesium – hypomagnesemia mg/dL	1.3 – 1.5	1.1 – 1.2	<1.1

Phosphorous – hypophosphatemia mg/dL	2.3 – 2.5	2.0 – 2.2	<2.0
CPK – mg/dL	400-1000	1001-1500	>1500
Albumin – Hypoalbuminemia g/dL	2.8 – 3.0	2.5 – 2.7	< 2.5
Total Protein – Hypoproteinemia g/dL	5.2 – <LLN	5.0 – 5.4	< 5.0
Alkaline phosphate – U/L	132-240	241– 360	>360

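### The dose-escalation criterion in Protocol Section 8.5 joins its two conditions with 'or' where 'and' is needed, so neither grade threshold withholds the next dose on its own

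*Protocol*

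**What the plan says.** Protocol Section 8.5 makes each new cohort wait until the preceding cohort's two-week safety data have been reviewed, and gives the SRC one criterion: it will "allow continuation if there are no product related grade 3 AEs or if there are fewer than two product related grade 2 AEs identified". The SRC is two people, the protocol principal investigator and the independent safety monitor (ISM), reviewing blinded data.

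The same section lists events that stop dosing until the Safety Monitoring Committee (SMC) has reviewed them. One is set by grade: "Any subject develops grade 3 laboratory abnormalities deemed related to the study drug". The others are:

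- death not due to trauma or accident;
- laryngospasm, bronchospasm or anaphylaxis within 24 hours;
- related Stevens-Johnson syndrome;
- generalized urticaria within 72 hours in two or more subjects;
- any related SAE;
- new EKG changes that a cardiologist calls significant;
- the case where "The SRC members are not unanimous in their agreement to proceed to the next dosing group", or cannot settle whether an event is related.

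Three further provisions matter. The Protocol Summary says the SMC will be convened for a clinically significant, drug-related AE, whereas Section 4 (repeated in SAP Section 3.1) leaves that to the SRC. Section 8.6.3 adds that "The ISM or principal investigator may request DMID to convene an ad hoc SMC meeting if a safety concern is identified". Section 8.5 lets DMID suspend dosing at any time.

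No section of either document restates the two thresholds with 'and'. Sections 4 and 8.6.2 require only that the data be analyzed.

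**The concern.** A criterion that names two toxicity thresholds is normally meant to fail when either is crossed. This one fails only when both are crossed together. On its wording, a cohort with several related Grade 3 clinical AEs and at most one Grade 2 AE qualifies for the next dose. So does a cohort with eight related Grade 2 AEs and no Grade 3.

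This is a first-in-human study rising from 0.5 to 60 mg/kg, and the outcomes left open include the toxicity the protocol anticipates. Section 2.1.1.4 names bone marrow and liver as the main target organs, so moderate ALT and neutrophil changes are relevant. Section 2.3.1 says "We expect that oxfendazole may have similar gastrointestinal events and rare allergic reactions". An SRC that follows the text would record the criterion as met in these cases. Any stop would then have to come from somewhere else.

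**Working it through.** **1. The plan's own figures.** No figure is attached to the SRC criterion. The nearest is Table 4 in Section 10.2, the probability of at least one event among eight active subjects, 1 − (1 − p)^8. At p = 0.05, 0.10, 0.18 and 0.25 this gives 33.7%, 57.0%, 79.6% and 90.0%, matching the stated 34%, 57%, 80% and 90%. The zero-event bound, 1 − 0.05^(1/8) = 31.2%, matches the stated 31%.

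**2. The logic.** Let G3 and G2 be the numbers of related Grade 3 and Grade 2 AEs in a cohort. As written, continue if G3 = 0 or G2 < 2. The complement is G3 ≥ 1 and G2 ≥ 2.

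| G3 | G2 | As written | With 'and' |
|---|---|---|---|
| 0 | 0 or 1 | continue | continue |
| 0 | 2 or more | continue | withhold |
| 1 or more | 0 or 1 | continue | withhold |
| 1 or more | 2 or more | withhold | withhold |

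This result needs no assumption about event rates.

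**3. What the separate halts leave open.** Setting aside everything on the Section 8.5 halting list, two outcomes have no grade-based gate:

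- (a) Related, non-serious clinical Grade 3 AEs off the list. An example is Grade 3 vomiting, defined in Appendix B as "Prevents daily activity or requires IV hydration", if it does not meet an SAE criterion.
- (b) Two or more related Grade 2 AEs with no Grade 3, such as ALT 106–175 U/L or neutrophils 1,000–1,499 per mm³ (Appendix B).

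**4. Do the laboratory follow-up rules close (b)?** Under Section 6.7, subjects with ALT or AST above 3 × ULN "will be asked to return for repeat testing within 72 hours of detection of the abnormal laboratory test". With the Appendix D limits, the ALT trigger is 3 × 41 = 123 U/L for men and 3 × 33 = 99 U/L for women, so it reaches much of the Grade 2 range in men and all of it in women. For neutrophils it starts only at Grade 3. Appendix A, note 3, goes lower: "Any abnormal laboratory result arising after administration of oxfendazole, and of moderate or greater severity, will be followed until results return to baseline value". Both provisions look after the affected subject. Neither conditions the next cohort's dose.

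**5. Illustrative frequencies (all rates assumed).** Subjects are taken as independent, with eight active per cohort (Section 4).

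*Outcome (a).* With p3 the chance that a subject has an off-list related clinical Grade 3 AE, P(at least one) = 1 − (1 − p3)^8 = 0.15, 0.34 and 0.57 at p3 = 2%, 5% and 10%. As written, the criterion is still met in these cohorts unless two or more Grade 2 AEs also occur.

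*Outcome (b).* Let p2 be the chance that a subject has at least one related Grade 2 AE. The criterion counts AEs, not subjects, so counting subjects gives a lower bound:

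1 − (1 − p2)^8 − 8·p2·(1 − p2)^7

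- p2 = 5%: 1 − 0.6634 − 0.2793 = 0.06
- p2 = 10%: 1 − 0.4305 − 0.3826 = 0.19

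One subject with Grade 2 ALT and Grade 2 AST already has two AEs, because Appendix B grades them on separate rows. If every affected subject had two, a single affected subject would be enough, and the figures become 1 − 0.95^8 = 0.34 and 1 − 0.90^8 = 0.57.

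Because review is blinded, events in the two placebo subjects may also be judged related. At the same rates with n = 10, the lower figures are 0.09 and 0.26 and the upper ones 0.40 and 0.65.

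**The case against.** The strongest reply is that escalation is never automatic. Either SRC member can force SMC review by disagreeing, and one of them is the ISM. The Protocol Summary says the SMC will be convened, not merely that it may be, for a clinically significant drug-related AE. Related Grade 3 vomiting needing IV fluids would plausibly count as clinically significant. It could also be an SAE under Section 8.2.3, which halts the study. The literal reading gives results so odd that two physicians would probably apply 'and' anyway.

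Much of this stands. A reader might infer that the study could escalate through any Grade 3 toxicity unchecked. The documents do not support that, because related Grade 3 laboratory results and related SAEs each stop dosing alone. Nor is SMC involvement in a clinically significant related AE purely optional, although Section 4 is softer than the Summary. It would also be wrong to read the three 'continue' rows in the table as a risk measure, since the four rows are not equally likely.

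What does not stand is the conclusion that the wording can be left. Every one of those safeguards, for outcomes (a) and (b), depends on someone judging an event clinically significant, asking for a meeting, or dissenting from a criterion that the text says is met. That 'and' was probably intended is a reason to write it.

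**Conclusion.** The criterion is wrong as written, and this follows from the sentence alone. The practical gap is narrower than the sentence suggests: related, non-serious clinical Grade 3 AEs off the halting list, and any number of related Grade 2 AEs without a Grade 3. There, stopping rests on judgement and not on a stated grade or count.

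That 'and' was meant is a strong inference, not something the documents state. The frequencies are illustrations on assumed rates and support no claim about how often the gap would be met in this trial. They exclude discretionary stops. Nothing is subtracted for Grade 2 events that may already halt by another route, such as bronchospasm within 24 hours.

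A reader might also infer that two related Grade 2 AEs ought to trigger SMC review. The documents do not say so: the bullet gives no consequence for failing the criterion, and the only halt defined by a toxicity grade is the one for Grade 3 laboratory abnormalities.

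**What to change.** In the Section 8.5 bullet, change 'if' to 'only if' and the joining 'or if there are' to 'and', so that the SRC may allow continuation only when there is no related Grade 3 AE and there are fewer than two related Grade 2 AEs. That completes the correction. Sending a failed criterion to the SMC, as Section 8.5 does for its halts, is a reasonable option for the sponsor but is not needed for it.

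No subjects or procedures are added. The cost is more pauses between cohorts. Seven dose levels mean six escalation decisions. If the assumed Grade 2 rate were the same at every dose, the chance of at least one pause would be 1 − (1 − q)^6, where q is the per-cohort figure. This is at least 0.30 (5%) or 0.71 (10%) on the subject-count lower bound, and 0.91 or 0.99 if each affected subject has two Grade 2 AEs. A constant rate over a 120-fold dose range (60 ÷ 0.5) is a simplification. If the sponsor finds this too frequent, it can raise the Grade 2 count openly, or count subjects instead of AEs.

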## 4 STUDY DESIGN

This Phase I study is a randomized, double-blind, placebo-controlled evaluation of the safety and PK of escalating single oral doses of oxfendazole (0.5, 1, 3, 7.5, 15, 30, 60 mg/kg) in healthy volunteers. The dose will be increased approximately three-fold (one-half log) at each increment, and each cohort will comprise 10 volunteers (8 drug, 2 placebo). Subjects will be monitored for 2 weeks after dosing, including monitoring the PK and metabolism of oxfendazole in blood and urine.

Two sentinel subjects (one randomized to receive study drug and the other to receive placebo) will be dosed and monitored 48 hours for adverse events prior to enrolling the remaining subjects in each cohort. If no drug-related serious adverse event or laboratory grade 3 study drug related events are observed within the 48 hour period, the remainder of the cohort will proceed with dosing. Each new cohort will be dosed only after the 2-week safety data for the preceding group have been analyzed. A Safety Review Committee (SRC) composed of the Protocol Principal Investigator and Independent Safety Monitor will review blinded safety data for the completed cohort. If a clinically significant AE is observed that is possibly drug related, the SRC will determine if an ad hoc SMC meeting should be called. Up to 70 volunteers (56 drug, 14 placebo) will complete the study. The Safety Monitoring Committee (SMC) will review the safety data either when or if the final dose is reached.

For the Phase I study, between 10 and 70 subjects (8:2 drug: placebo in each cohort receiving increasing doses) will be enrolled. This number should be small enough to perform the study safely and efficiently, yet large enough for an estimation of the PK, metabolism, and the identification of any common side effects of oxfendazole.

The study will be conducted on an outpatient basis at the University of Iowa. Screening for subject recruitment will continue throughout the study until the requisite number of volunteers is enrolled. Each subject will be evaluated over a 2 week period. Projected duration of subject participation will be 3-6 weeks of face to face visits, including the screening period. It is anticipated that it will take 18 months to finish the study.

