## 8.2.3 Serious Adverse Events

**Serious Adverse Event (SAE):**

An adverse event or suspected adverse reaction is considered “serious” if, in the view of either the investigator or sponsor, it results in any of the following outcomes:

- Death,
- a life-threatening adverse event\*,
- inpatient hospitalization or prolongation of existing hospitalization,
- a persistent or significant incapacity or substantial disruption of the ability to conduct normal life functions, or,
- a congenital anomaly/birth defect.
- Important medical events that may not result in death, be life-threatening, or require hospitalizations may be considered serious when, based upon appropriate medical judgment they may jeopardize the subject and may require medical or surgical intervention to prevent one of the outcomes listed in this definition. Examples of such medical events include allergic bronchospasm requiring intensive treatment in an emergency room or at home, blood dyscrasias or convulsions that do not result in inpatient hospitalization, or the development of drug dependency or drug abuse.

\* Life-threatening adverse event. An adverse event is considered “life-threatening” if, in the view of either the investigator or sponsor, its occurrence places the subject at immediate risk of death. It does not include an adverse event, had it occurred in a more severe form, might have caused death.

All SAEs will be:

- Assessed for severity and relationship to study product and alternate etiology (if not related to study product) by a licensed study physician listed on the Form FDA 1572 as the site principal investigator or sub-investigator.
- Recorded on the appropriate SAE form and eCRF.
- Followed through resolution or stabilization by a study physician licensed to make medical diagnoses and listed on the Form FDA 1572 as the site principal investigator or sub-investigator.
- Reviewed and evaluated by an Independent Safety Monitor (ISM), the SMC (periodic review unless related), DMID personnel including the medical monitor, and the IRB.

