#### 8.3.1 Serious Adverse Events

Any AE that meets a protocol-defined serious criterion must be submitted immediately (within 24 hours of site awareness) on an SAE form to the DMID Pharmacovigilance Group, at the following address:

**DMID Pharmacovigilance Group  
Clinical Research Operations and Management Support (CROMS)  
[name] [name] 650  
Bethesda, MD 20814, USA**

**SAE Hot Line: [name] (US) or [name] (outside US)  
SAE FAX [contact] (US) or [name] (outside US)  
SAE Email Address: [[contact]](mailto:[contact])**

Other supporting documentation of the event may be requested by the DMID Pharmacovigilance Group and should be provided as soon as possible.

The DMID medical monitor and clinical protocol manager will be notified of the SAE by the DMID Pharmacovigilance Group. The DMID medical monitor will review and assess the SAE for regulatory reporting and potential impact on study subject safety and protocol conduct.

At any time after completion of the study, if the investigator becomes aware of an SAE that is suspected to be related to study product, the investigator will report the event to the DMID Pharmacovigilance Group.

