### **8.6.2 Safety Review Committee (SRC)**

An SRC composed of the Protocol Principal Investigator and Independent Safety Monitor will review blinded safety data for each completed cohort. Each new cohort will be dosed only after the 2-week safety data for the preceding group have been analyzed.

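### Minor: the automatic halt for a drug-related SAE lapses at each subject's last visit while higher doses are still to come, and the final-visit window can end AE review two days short of the 14-day primary endpoint

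*Protocol*

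**What the plan says.** **Halting rule.** Protocol Section 8.5 lists events that stop enrollment, dosing and procedures until the SMC has reviewed them and recommended going on. The trigger for serious events is "Any subject experiences a study drug-related SAE from the time of receipt of study drug through the subject's last study visit". The trigger for deaths not due to trauma or accident has the same end point. Acute allergic events have windows of 24 or 72 hours. Four triggers have no end date: drug-related Stevens Johnson Syndrome, EKG changes that a cardiologist judges significant, related grade 3 laboratory abnormalities, and disagreement within the Safety Review Committee (SRC) on escalation or relatedness.

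**Last visit and escalation.** Section 6.4 puts Visit 08 at Day 15 ±2. A subject who withdraws is offered an Early Termination Visit (6.5). Section 4 describes "escalating single oral doses of oxfendazole (0.5, 1, 3, 7.5, 15, 30, 60 mg/kg) in healthy volunteers", and Section 8.6.2 says "Each new cohort will be dosed only after the 2-week safety data for the preceding group have been analyzed".

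**Later events.** Section 8.3.1 requires SAEs to be submitted within 24 hours of site awareness. It also requires a report, at any time after study completion, "if the investigator becomes aware of an SAE that is suspected to be related to study product". It adds: "The DMID medical monitor will review and assess the SAE for regulatory reporting and potential impact on study subject safety and protocol conduct". Section 8.2.3 has the SMC review related SAEs outside its periodic cycle. Section 8.5 adds "DMID retains the authority to suspend additional enrollment and study interventions/administration of study product during the entire study, as applicable", and Section 8.6.3 adds "The ISM or principal investigator may request DMID to convene an ad hoc SMC meeting if a safety concern is identified". The Protocol Summary has the SMC convened for a clinically significant drug-related AE. Section 4 leaves the call for an ad hoc meeting on a possibly related AE to the SRC.

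**AE window.** The primary endpoint (3.2) counts related AEs within 14 days of the dose. Section 8.3 documents AEs for approximately 14 days. Appendix A schedules no contact after Visit 08, and Section 6.6 allows later visits only to follow AEs that arose during the study period.

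**The concern.** This is the first trial of oxfendazole in humans, and the doses rise in sequence. A default halt ensures that a related serious event pauses the next, higher dose until the SMC has looked at it, without anyone having to decide to stop. Because each cohort waits for the preceding group's two-week data, higher doses are given after that cover has ended for earlier subjects. The list is also uneven: a late related grade 3 laboratory value halts the study by rule, but most other late related SAEs do not.

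The second point concerns ascertainment. If the final AE interview takes place before 14 days have passed, the primary endpoint and the two-week data that the SRC reviews rest on an incomplete window for that subject. The two points also meet. In a subject last seen on Day 13, a related SAE starting 13 days after dosing falls inside the primary endpoint but outside the halting trigger.

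**Working it through.** **1. Day count.** Dosing is on Day 1, so hours after dosing = (study day − 1) × 24. For Days 2, 3, 4, 6, 8 and 15 this gives 24, 48, 72, 120, 168 and 336 h, which matches the nominal times in SAP Exhibits 2 to 4.

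**2. Final-visit window (6.4).**
- Day 13: 12 × 24 = 288 h, or 12 days. This leaves 2 of the 14 endpoint days uncovered (2/14 = 14.3%).
- Day 14: 13 × 24 = 312 h, or 13 days. This leaves 1 of 14 (7.1%).
- Day 15: 336 h, or 14 days, so the endpoint is covered.
- Day 17: 16 × 24 = 384 h, or 16 days, so the endpoint is covered.

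**3. Dosing after halt cover ends.** The dose steps are 1/0.5 = 2, 3/1 = 3, 7.5/3 = 2.5, 15/7.5 = 2, 30/15 = 2 and 60/30 = 2. The fastest schedule assumes a 2-day sentinel hold, then follow-up of the rest of the cohort to Visit 08, with no time for review or recruitment.
- Visit 08 on Day 15: 2 + 14 = 16 days per cohort. From cohort k's final Visit 08 to the last dose in cohort 7 is (6 − k) × 16 + 2 days, that is 82, 66, 50, 34, 18 and 2 days for k = 1 to 6.
- Every Visit 08 on Day 13: 2 + 12 = 14 days per cohort. For k = 1 this is 5 × 14 + 2 = 72 days.

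After cohort 1, 70 − 10 = 60 subjects remain to be dosed, 56 − 8 = 48 of them on drug. After cohort 6, 10 remain, 8 of them on drug.

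**4. Possible effect of early final visits.** Protocol Table 4 gives 80% for seeing at least one event at a true rate of 0.18 with N = 8. Recomputed: 1 − 0.82^8 = 79.6%, which rounds to the stated figure.

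The share of subjects seen early is unknown. For illustration, assume that every AE is a symptom AE, that onset is uniform over 14 days (probably pessimistic for a single dose), and that a share s of subjects is last reviewed d days early. Then p′ = 0.18 × (1 − s × d/14), and the chance of seeing at least one event is 1 − (1 − p′)^8.

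| s | Last review Day 13 (d = 2) | Last review Day 14 (d = 1) |
|---|---|---|
| 10% | 79.0% | 79.3% |
| 40% | 77.4% | 78.5% |
| 100% | 73.8% | 76.8% |

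This model does not apply to laboratory or EKG AEs. After dosing these are seen only at scheduled checks (laboratory tests on Days 4, 8 and 15, and on Day 3 for sentinels; EKG on Days 4, 8 and 15), so moving the last check changes which moment is sampled.

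**The case against.** The strongest reply is that a late related SAE already meets several layers of oversight. It is reported, the medical monitor assesses it, and it goes to the SMC outside the periodic cycle. The Protocol Summary has the SMC convened for a clinically significant drug-related AE and sets no time limit. The SRC consists of the principal investigator and the independent safety monitor, so one dissenting member halts escalation automatically. The sponsor can also suspend dosing at any time. All of this stands. A reader might infer that late related SAEs escape oversight, or that escalation would go on regardless, and the documents do not support that. What remains is narrower. Convening the SMC does not itself stop dosing, the SRC trigger needs a disagreement, and suspension needs a decision.

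A reader might also take the restriction to post-completion reports in Section 8.3.1 to mean that an SAE between a subject's last visit and study completion goes unreported. That section's opening requirement is tied to site awareness and sets no end date, so this reading is not supported either. Nor do the documents show a delayed-toxicity signal after a single dose: Section 2.3.1 says the white cell count recovers rapidly once dosing stops.

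On the visit window, Section 8.3 speaks only of approximately 14 days and the analysis is descriptive (10.4), so a ±2 allowance is ordinary practice. That limits the importance of the point, but the endpoint itself is defined as within 14 days. It would also be tempting to say that an early last visit can only lower the AE rate. That holds for symptom AEs. A Day 13 blood draw or EKG could instead catch a transient abnormality that has gone by Day 15.

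**Conclusion.** Both points hold, and both are minor.

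- **Halting rule.** A related SAE that starts after the subject's last visit and meets no other trigger does not by rule pause dosing pending SMC review. On the fastest schedule this exposure lasts 72 to 82 days after cohort 1's last visit. A reader might take 82 days as the minimum, but the visit window allows 72. Review and recruitment time would lengthen the interval. These are durations only, because the documents give no rate of late related SAEs.
- **AE window.** The final review may fall 12 or 13 days after dosing, leaving 1 or 2 of the 14 endpoint days uncovered for symptom AEs in those subjects. The bias in that component is downward and probably small. With 10% of subjects last seen on Day 13, the illustrative chance of seeing at least one event falls from 79.6% to 79.0%. The 73.8% figure needs every subject to be seen on Day 13, together with uniform onset. For laboratory and EKG AEs the direction is not established.

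**What to change.** 1. In Section 8.5, reword the serious-event trigger to apply to any study drug-related SAE reported while any study dosing remains. A related death is itself a related SAE, so the death trigger needs no separate change. Cost: a wording amendment and an occasional extra SMC review.
2. Keep the Day 15 ±2 window and add a phone AE check on or after Day 15 for any subject whose Visit 08 falls on Day 13 or 14. This covers symptom AEs and SAEs only; a call cannot replace a laboratory test or an EKG. Cost: one call per subject seen early.

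Neither change adds clinic visits, laboratory tests or subjects.
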